4.1 Inclusion Criteria

- 101 Subject has provided informed consent prior to initiation of any study-specific activities/procedures
- 102 Male or female age ≥ 18 years at the time of informed consent
- 103 Pathologically documented, definitively diagnosed, advanced CRC, pancreatic cancer or NSCLC that is refractory to standard treatment, or the subjects have been intolerant to or refuse standard treatment. The select tumor types must also meet the following criteria:
- Part 1 and Group 1: advanced MMR-proficient CRC subjects naïve to anti-PD-1/PD-L1/CSF-1/CSF-1R therapies
 - Part 1 and Group 2: advanced pancreatic cancer subjects with good performance status (defined as ECOG 0-1, good pain management and adequate nutritional intake) naïve to anti-PD-1/PD-L1/CSF-1/CSF-1R therapies
 - Part 1 and Group 3: advanced NSCLC subjects with *low* ($< 50\%$) tumor PD-L1- expression naïve to anti-PD-1/PD-L1/CSF-1/CSF-1R therapies
 - Part 1 and Group 4a: NSCLC subjects with *low* ($< 50\%$) tumor PD-L1-expression who are anti-CSF-1/CSF-1R naïve and have not responded to (disease progression or stable disease > 6 months) or have relapsed during monotherapy with anti-PD-1/PD-L1 therapies
 - Part 1 and Group 4b: NSCLC subjects with *high* ($\geq 50\%$) tumor PD-L1-expression who are anti-CSF-1/CSF-1R naïve and have not responded to (disease progression or stable disease > 6 months) or have relapsed during monotherapy with anti-PD-1/PD-L1 therapies
- 104 Subject must have radiographically and/or clinically measurable disease per RECIST 1.1 ([Eisenhauer et al, 2009](#)). Index lesions must not be chosen from a previously irradiated field unless there has been radiographic tumor progression in that lesion prior to enrollment. See Note: [Appendix D](#) for index lesion and non-index lesion criteria.
- 105 ECOG performance status of 0 - 1
- 106 Adequate organ function determined prior to enrollment, defined as follows:
- Hematological
 - ANC $\geq 1.5 \times 10^9/L$
 - platelet count $\geq 100 \times 10^9/L$
 - hemoglobin ≥ 9 g/dL (without need for hematopoietic growth factor or transfusion support)
 - Renal
 - serum creatinine ≤ 1.5 x upper limit of normal (ULN), OR 24 hr creatinine clearance ≥ 60 mL/min for subject with creatinine levels > 1.5 x ULN.

(Note: Creatinine clearance need not be determined if the baseline serum creatinine is within normal limits. Creatinine clearance should be determined per institutional standard).

- Hepatic

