Appendix D. Modified Immune-Related Response Criteria in Solid Tumors (irRECIST)

The Immune-related Response Criteria (irRC) based on bidimensional measurements were derived from WHO/RECIST to serve as guidelines to systematically characterize additional patterns of response in patients with advanced melanoma receiving ipilimumab therapy and to allow the potential delayed clinical response to immune-enhancing therapies to be captured more accurately (Wolchok JD et al., 2009). Recent evaluation showed that irRC using unidimensional measurements provided highly concordant tumor response assessment and less measurement variability compared with bidimensional measurements (Nishino M et al., 2013). This study will utilize a modified criteria (irRECIST), adapting the immune-related response criteria to conventional RECIST 1.1 (Eisenhauer et al, 2009) as outlined below.

Antitumor response based on total measurable tumor burden

- For irRECIST, only index and measurable new lesions are taken into account (in contrast to conventional RECIST 1.1, which does not require the measurement of new lesions, nor do they include new lesion measurements in the characterization of evolving tumor burden).

Tumor burden assessment:

- All measurable and non-measurable lesions should be assessed at screening and at the defined tumor assessment time points.
 - At baseline tumor assessment: tumor burden is the sum of the longest diameters (SLD) of all index lesions (5 lesions per organ, up to 10 total lesions).
 - At each subsequent tumor assessment: tumor burden is the SLD of the index lesions and of new, measurable lesions (≥ 10 mm in the longest diameter; up to 5 new lesions per organ and up to 10 total lesions) added together
 - Tumor burden = $SLD_{\text{index lesions}} + SLD_{\text{new, measurable lesions}}$

Time point response assessment using modified irRECIST

Percentage changes in tumor burden per assessment time point describe the size and growth kinetics of both conventional and new lesions as they appear. At each tumor assessment, the response in index and new measurable lesions is defined based on the change in tumor burden (after ruling out irPD). Decreases in tumor burden must be assessed relative to baseline measurements (ie, the SLD of all index lesions at screening).

Definitions:

- Methods of measurement:
 - The same imaging modality, method of assessment, and technique must be used throughout the study to characterize each identified and reported lesion.

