 - MRI or CT scans should be performed with contiguous slice thickness of 5 mm or less according to the Imaging Manual. Subjects should be evaluated at screening for tolerance to MRI/CT IV contrast. Subjects intolerant of CT IV contrast ie, allergy or renal insufficiency should be imaged using non-contrast CT for the chest and MRI (with or without contrast) for the abdomen and pelvis to enable the best detection of disease throughout the study starting at baseline. If a subject develops a medical contradiction to the MRI/CT IV contrast while on study, preapproval of the sponsor is needed to switch from contrast enhanced MRI to non-contrast MRI or to CT (and vice versa).
 - If a combined PET/CT scan is performed at the discretion of the investigator at baseline and subsequent timepoints, the CT portion of that exam should not be substituted for the dedicated diagnostic CT exams required by this protocol unless the investigator or the site radiologist can document that the CT performed as part of a PET/CT is of identical diagnostic quality to the diagnostic CT as described in the Imaging Manual, then the CT portion of the PET/CT can be used for tumor measurements.
 - Pathological lymph nodes (short axis >10 mm) should be assessed by MRI/CT. Only nodes with short axis ≥ 15 mm are to be included as measurable lesions.
 - Patients with suspected brain metastases will also undergo MRI of the brain.
 - All baseline evaluations should be performed as closely as possible to the beginning of treatment, and not more than 28 days before the beginning of the treatment (cycle 1 day 1).
- Measurable disease: Subject must have radiographically measurable disease per RECIST 1.1 ([Eisenhauer et al, 2009](#)).
 - Measurable lesions:
 - Lesions with clear borders that can be measured accurately in one dimension (longest diameter ≥ 10 mm as measured by MRI/CT with scan slice thickness ≤ 5 mm).
 - Pathologic lymph nodes are measurable when the longest diameter perpendicular to the long axis (short axis) is ≥ 15 mm on MRI/CT.
 - Must exclude cystic lesions, pleural/pericardial effusions and ascites.
 - Non-Measurable lesions:
 - All other lesions, including small lesions (longest diameter < 10 mm or pathological lymph nodes with ≥ 10 mm but < 15 mm short axis) and other truly non-measurable lesions are considered non-measurable and characterized as non-index lesions.

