 - Cystic lesions thought to represent cystic metastases can be considered as measurable lesions, if they meet the definition of measurability described above. However, if non-cystic lesions are present in the same subject, these are preferred for selection as index lesions. If a cystic lesion is clearly cancerous and has both cystic and solid components, then the complete lesion should be measured including both components without excluding the cystic portion of a cystic tumor lesion when measuring.

- Lesions with prior local treatment:
 - Tumor lesions situated in a previously irradiated area, or an area subject to other loco-regional therapy, should not be considered measurable unless there has been demonstrated progression in the lesion.
- Index lesions: all measurable lesions up to a maximum of 5 lesions per organ and 10 lesions in total, representative of all involved organs, are to be identified as Index lesions, recorded and measured. Index lesions are to be selected on the basis of their size and their suitability for accurate repeated measurements by imaging, and most representative of the subject's tumor burden and overall disease status.
- New lesions: New measurable lesions (ie, accurately and serially measurable in at least 1 dimension ≥ 10 mm for non-nodal lesions or the short axis is ≥ 15 mm for nodal lesions). The new measurable lesions should be selected on the basis of their size and suitability for accurate repeated measurements by CT or MRI. If there are more than 10 measurable new lesions detected at an imaging time point for a subject, lesions not selected for measurements would be considered non-Index lesions.
- Non-Index lesions: measurable lesions, other than index lesions, and all sites of non-measurable disease, will be identified as non-index lesions. Non-index lesions will be evaluated at the same assessment time points as the index lesions. In subsequent assessments, changes in non-index lesions will contribute only in the assessment of complete response.
 - Pathologic lymph nodes with short axis ≥ 10 mm but < 15 mm at baseline should be considered as non-index lesions
- Unable to evaluate (UE): Any lesion present at baseline which was not assessed or was unable to be evaluated leading to an inability to determine the status of that particular tumor for that time point
- Not Available (NA): Scan not available
- Not Done (ND): Radiographic imaging were not performed at this time point to evaluate the index lesions

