 - irPD – increases in number or size of non-index lesion(s) does not constitute progressive disease. New lesions that are measurable up to 5 new lesions per organ and 10 total) are included in the calculation of tumor burden in response assessments
- Overall response
 - irCR – complete disappearance of all lesions (whether measurable or not, and no new lesions)
 - Confirmation by a repeat, consecutive assessment no less than 4 weeks from the date of the first documented response
 - irPR – decrease in tumor burden \geq 30% relative to baseline.
 - Confirmation by a repeat, consecutive assessment no less than 4 weeks after the first documentation
 - irSD – not meeting criteria for irCR or irPR, in the absence of irPD
 - irPD – increase in tumor burden \geq 20% relative to nadir (minimum recorded tumor burden) and at least 5 mm absolute increase compared to nadir.
 - Confirmation by a repeat, consecutive assessment no less than 4 weeks from the date of the first documented assessment.

Response confirmation:

- irCR and irPR:
 - the repeat confirmation scan may be performed any time after 4 weeks from the first suspected radiologic evidence of response and may be delayed until the next scheduled scan to avoid necessary procedures
- irPD:
 - In subjects who have initial evidence of radiological PD by irRECIST (irPD on one scan), it is at the discretion of the PI whether to continue a subject on study treatment until repeat imaging is obtained based on their assessment of clinical stability. Subjects may receive study treatment and tumor assessment should be repeated ≥ 4 weeks later in order to confirm irPD per site assessment.
 - In determining whether or not the tumor burden has increased or decreased per irRECIST, the local site investigator should consider all index as well as any incremental new measureable lesion(s).
 - irPD is confirmed at repeat imaging (irPD on two consecutive scans at least 4 weeks apart) if tumor burden remains $\geq 20\%$ and at least 5 mm absolute increase compared to nadir

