### **7.1 Safety Analysis Set**

The Safety Analysis Set will consist of all subjects that are enrolled and receive at least 1 dose of AMG 820.

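### Criterion 104 allows entry on clinically measurable disease alone, but Appendix D builds the primary response endpoint only on lesions measured by MRI/CT

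*Protocol*

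**What the plan says.** **Eligibility.** Protocol Section 4.1, criterion 104: "Subject must have radiographically and/or clinically measurable disease per RECIST 1.1". The same criterion points to Appendix D for what counts as an index or non-index lesion.

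**Endpoint.** Protocol Appendix D: "Subject must have radiographically measurable disease per RECIST 1.1". It defines a measurable lesion by its longest diameter "as measured by MRI/CT with scan slice thickness" of at most 5 mm, and nodes by their short axis on MRI/CT. Index lesions are chosen for size and "suitability for accurate repeated measurements by imaging". At baseline, "tumor burden is the sum of the longest diameters (SLD) of all index lesions". Partial response is a fall of at least 30% in that sum relative to baseline. Appendix D gives no rule for a lesion measured by caliper or on examination.

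**Study design text.** Section 3.1 of the protocol, repeated in Section 3.1 of the SAP, nevertheless plans clinical measurement of lesions alongside MRI or CT at each tumor assessment.

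**Denominator.** Protocol Section 10.1.2 and SAP Section 7 use the Safety Analysis Set for every endpoint unless noted otherwise. SAP Section 7.1 defines it as "all subjects that are enrolled and receive at least 1 dose of AMG 820". Neither document defines a response-evaluable set. The futility and success rules in Protocol Section 10.2 and SAP Section 3.2 are written in numbers of subjects enrolled.

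**The concern.** The eligibility criterion and the primary endpoint use different definitions of measurable disease. A site that reads criterion 104 literally can enroll a subject whose only measurable lesion is measured on examination. Appendix D then has nothing to measure: no index lesion, no baseline sum of diameters, and so no percentage fall.

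Such a subject adds one to the denominator and can add little or nothing to the numerator. In small two-stage groups with first stages of 18, 10, 19, 10 and 10, a single subject of this kind can matter. In Group 2 and in each Group 4 sub-group, no responder among the first 10 triggers the futility recommendation. What is at stake is a missed signal of activity. A false positive becomes less likely, not more.

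**Working it through.** **1. The passages side by side**

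| Item | Criterion 104 | Appendix D |
|---|---|---|
| Measurable disease | Radiographic and/or clinical | Radiographic |
| Measurement method | Not given; refers to Appendix D for lesion types | MRI/CT only |
| Clinical measurement rule | None | None |

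**2. What a subject with no MRI/CT-measurable lesion can be scored as**

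- *Partial response:* "irPR – decrease in tumor burden" of at least 30% relative to baseline. With no baseline sum this cannot be calculated.
- *Complete response:* unclear. The overall-response text asks for "complete disappearance of all lesions (whether measurable or not, and no new lesions"), which could be met when only non-index lesions exist. The overall-response table asks for a 100% fall in the measured burden. It has no row for a subject without index lesions, and the nearest rows (burden not available, not done or not evaluable) return unable to evaluate.
- *Progression:* not excluded. New measurable lesions of 10 mm or more are added to the burden, and going from nothing to 10 mm exceeds the 5 mm absolute requirement, although a percentage of zero is undefined.

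**3. The plan's own power**

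Inputs from Protocol Section 10.2: stage 1 size n1, stop at r1 or fewer responders, total n, success at r + 1 or more.

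Power(p) = Σ over x from r1 + 1 to n1 of Bin(x; n1, p) × P[Bin(n − n1, p) ≥ r + 1 − x]

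| Group | r1/n1 | Success | Null / target ORR | Type I error | Power |
|---|---|---|---|---|---|
| 1 | 2/18 | ≥ 8 of 43 | 10% / 25% | 4.8% | 80.0% |
| 2, 4a, 4b | 0/10 | ≥ 4 of 29 | 5% / 20% | 4.7% | 80.1% |
| 3 | 3/19 | ≥ 13 of 55 | 15% / 30% | 4.8% | 80.1% |

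The stated 80% and 5% are reproduced.

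**4. One subject who cannot respond**

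Assumptions: the target rate applies to the other subjects, and this subject stays in the count. Replace n1 by n1 − 1 responding subjects (stage 1) or n − n1 by n − n1 − 1 (stage 2), and keep the cut-offs. Random placement is the average weighted by stage size.

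| Group | None | In stage 1 | In stage 2 | At random |
|---|---|---|---|---|
| 1 | 80.0% | 76.7% | 78.9% | 78.0% |
| 2, 4a, 4b | 80.1% | 76.7% | 78.6% | 77.9% |
| 3 | 80.1% | 76.5% | 78.9% | 78.1% |

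For example, Group 2 at random: (10 × 76.668 + 19 × 78.624) / 29 = 77.9%.

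The chance in Group 2 of a futility recommendation at a true 20% rises from 0.8^10 = 10.7% to 0.8^9 = 13.4% if the subject is in stage 1.

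**5. Range over an unknown fraction f**

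The documents give no frequency, so f is an assumption. The effective response rate is p × (1 − f) in both stages.

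| f | Group 1 | Groups 2, 4a, 4b | Group 3 |
|---|---|---|---|
| 2% | 78.2% | 78.8% | 77.8% |
| 5% | 75.3% | 76.8% | 74.0% |
| 10% | 69.7% | 73.0% | 66.7% |

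At f = 10%, type I error falls to 2.8%, 3.4% and 2.3%.

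**The case against.** The strongest reply is that the affected subject may not exist. Criterion 104 refers to Appendix D, and Appendix D demands radiographically measurable disease, so the two read together may already exclude this subject. Screening imaging covers chest, abdomen and pelvis, and assessments must include all other sites of disease. A lesion found on examination that also meets the size rule on imaging is an ordinary index lesion. This largely stands: it makes the case rare. It does not remove the conflict. The cross-reference concerns lesion types and does not clearly override the clinical alternative, and Section 3.1 of both documents keeps clinical measurement alive.

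A reader might infer three stronger things, none of which the documents support:

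- *That these subjects can never be responders.* Only partial response is clearly out of reach. For complete response the Appendix D text and table point different ways.
- *That the 80% power is wrong.* Section 10.2 states the 25%, 20% and 30% as rates anticipated in the group. If they are averages over everyone treated, including any subject who cannot respond, 80% holds.
- *That a stage 1 shortfall stops a group automatically.* Protocol Sections 10.2 and 10.3.1 leave the decision to the Dose Level Review Team after review of all data. Section 10.2 words the Group 3 stop more firmly, but the general rule and Section 3.1.2 leave it to the same team.

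**Conclusion.** The conflict between criterion 104 and Appendix D is real and bears on the primary efficacy endpoint. Its practical weight is small.

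The size is conditional on two things: that a subject whose only measurable lesion cannot be measured on MRI/CT is enrolled and dosed, and that the anticipated response rates are rates among MRI/CT-measurable subjects. The figures also score that subject as a non-responder. One such subject in a group then costs about 2 points of power on average, with a range of 1.1 to 3.6 points depending on group and stage. The frequency is not in the documents; in these tumor types it is probably low. The stated designs are arithmetically sound. This is a worthwhile clean-up and does not threaten the trial's conclusions.

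**What to change.** 1. In criterion 104, delete the words "and/or clinically" so that eligibility requires at least one MRI/CT-measurable index lesion, as Appendix D does.
2. Reconcile the clinical-measurement wording in Section 3.1 of the protocol and of the SAP with Appendix D. If clinical measurement is meant to count toward response, Appendix D needs a rule for it; otherwise the text should say that it does not enter the tumor burden.
3. For subjects already enrolled, add a sentence to the SAP on how a dosed subject without a baseline index lesion is counted in the response rate, and settle whether complete response is possible for such a subject.

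The cost is a few words in each place. The downside is that a rare subject becomes ineligible. The rationale for Amendment 2 records that the sponsor has decided to discontinue investigating the combination, so the eligibility edit may have little prospective effect. The SAP sentence remains useful for the final analysis.

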4.2 Exclusion Criteria

201 Has known active central nervous system (CNS) metastases and/or carcinomatous meningitis. Subjects with previously treated brain metastases may participate provided they are stable (without evidence of progression by imaging for at least four weeks prior to the first study dose and neurologic symptoms should have returned to baseline), have no evidence of new or progressing brain lesions, and are not using steroids $> 10 \text{ mg}$ prednisone equivalent for at least 7 days prior to trial treatment. This exception does not include carcinomatous meningitis which is excluded regardless of clinical stability.

202 History of other malignancy within the past 2 years with the following exceptions:

- malignancy treated with curative intent and with no known active disease present and has not received chemotherapy for ≤ 2 years before enrollment and felt to be at low risk for recurrence by the treating physician

- adequately treated non-melanoma skin cancer, cervical carcinoma *in situ*, superficial or *in situ* carcinoma of the bladder or breast ductal carcinoma *in situ*, without evidence of disease for any of these at the time of enrollment
 - prostatic intraepithelial neoplasia without evidence of prostate cancer at the time of enrollment
- 203 Subject has history of interstitial lung disease, (non-infectious) pneumonitis that required steroids, or current pneumonitis.
- 204 History or evidence of other active autoimmune diseases that has required prolonged systemic treatment in past 2 years (ie, with use of disease modifying agents such as corticosteroids or immunosuppressive drugs).
- Note: Replacement therapy (eg, thyroxine, insulin, or physiologic corticosteroid replacement therapy for adrenal or pituitary insufficiency, etc.) is not considered a form of systemic treatment.
- 205 Evidence of clinically significant immunosuppression such as the following:
- organ transplant or prior stem cell transplantation
 - any severe congenital or acquired cellular and/or humoral immune deficiency
 - other signs or symptoms of clinical immune system suppression or diagnosis of immunodeficiency
 - concurrent opportunistic infection
- 206 receiving systemic immunosuppressive therapy (> 2 weeks) within 7 days prior to the first dose of study treatment, including oral steroid doses > 10 mg/day of prednisone or equivalent except for management of adverse events during the course of the study. Subjects that require intermittent use of bronchodilators or local steroid injection will not be excluded from the study.
- 207 receiving systemic immunostimulatory agents within 6 weeks or five half-lives, whichever is shorter, prior to first dose of study treatment (except anti PD-1/PD-L1 treatment if recruited into Group 4a or 4b).
- 208 Evidence of active infection within 2 weeks prior to first dose of study treatment.
- 209 Prior chemotherapy, radiotherapy, biological cancer therapy or major surgery within 28 days prior to enrollment. Note: patients may have received anti PD-1/PD-L1 treatment if recruited into group 4a and 4b (refractory/relapsed on anti-PD-1/PD-L1 + naïve to CSF-1/CSF-1R treatment).
- 210 Currently participating or has participated in a study (treatment period only) of an investigational agent or used an investigational device within 28 days of enrollment.
- 211 Adverse event due to cancer therapy administered more than 28 days prior to enrollment that has not recovered to CTCAE grade 1 or better. Note: Subjects with ≤ grade 2 neuropathy and alopecia are an exception to this criterion and may qualify for the study.
- 212 Expected to require other cancer therapy while on study (eg, need of local palliative radiation treatment to the site of bone and other metastasis will be considered sign of clinical progression).
- 213 Other investigational procedures while participating in this study are excluded.
- 214 Positive for human immunodeficiency virus (HIV).

- 215 Hepatitis B and C based on the following results:
- Positive for hepatitis B surface antigen (HBsAg) (indicative of chronic hepatitis B or recent acute hepatitis B).
 - Negative HBsAg and positive for hepatitis B core antibody: hepatitis B virus DNA by polymerase chain reaction (PCR) is necessary. Detectable hepatitis B virus DNA suggests occult hepatitis B.
 - Positive Hepatitis C virus antibody (HCVAb): hepatitis C virus RNA by PCR is necessary. Detectable hepatitis C virus RNA suggests chronic hepatitis C
- 216 Received live vaccine within 28 days prior to enrollment.
- 217 Men of reproductive potential and women of childbearing potential who are unwilling to practice a highly effective method(s) of birth control while on study through 4 months after receiving the last dose of study drug. Highly effective methods of birth control are defined as those which result in a low failure rate (ie, less than 1% per year) when used consistently and correctly such as implants, injectables, combined oral contraceptives, intrauterine devices (IUDs), sexual abstinence or vasectomised partner.
- Note: Men and women who do not meet the definitions below are considered to be of reproductive potential or childbearing potential respectively.
- Men of non-reproductive potential are defined as having azoospermia, whether due to having had a vasectomy or due to an underlying medical condition.
 - Women not of childbearing potential are defined as: Any female who is postmenopausal defined as at least 12 months with no menses without an alternative medical cause; in women < 45 years of age, a high follicle stimulation hormone [FSH] level in the postmenopausal range may be used to confirm a postmenopausal state in women not using hormonal contraception or hormonal replacement therapy; in the absence of 12 months of amenorrhea, a single FSH measurement is sufficient OR have had a hysterectomy and/or bilateral oophorectomy, or bilateral salpingectomy at least 6 weeks prior to screening, OR has a congenital or acquired condition that prevents childbearing.
- 218 Women who are lactating /breastfeeding or who plan to breastfeed while on study through 4 months after receiving the last dose of study drug.
- 219 Women with a positive pregnancy test.
- 220 Women planning to become pregnant while on study through 4 months after receiving the last dose of study drug.
- 221 Subject has known sensitivity to any of the products or components to be administered during dosing.

- 222 Subject likely to not be available to complete all protocol-required study visits or procedures, and/or to comply with all required study procedures to the best of the subject and investigator's knowledge.
- 223 History or evidence of psychiatric, substance abuse, or any other clinically significant disorder, condition or disease (with the exception of those outlined above) that, in the opinion of the investigator or sponsor physician, if consulted, would pose a risk to subject safety or interfere with the study evaluation, procedures or completion.

